14.5 Accrual Rate and Study Duration

The Phase I portion of the study will require a minimum 4 patients and at maximum 36 patients. The Phase I portion will require 12 to 18 months to complete.

Phase II portion of the study will require 20-30 months to complete at an expected accrual rate of 1 per month in each of strata 1 and 2.

14.6 Toxicity Monitoring during Phase II

A minimum of 40 and possibly as many as 90 patients will be enrolled in strata 1, 2 and 3 combined during Phase II. Toxicity monitoring will continue during Phase II as described below, with patients in strata 1 through 3 combined in this analysis.

The primary endpoint for toxicity monitoring will be the occurrence of DLT during the first course of treatment. If the number of DLTs occurring in the first course of treatment equals or exceeds the number in the table below, the study will be suspended to accrual pending review of toxicities by the study committee, in consultation with the DSMC, to determine whether the study should continue as planned, be amended, or be terminated. This monitoring rule has at most 14% Type I error for true DLT rates of 15% or lower, which are considered acceptable, at least 80% power to detect DLT rates of 25% or more, and at least 95% power to detect DLT rates of 30% or more. The average numbers of patients that would be treated under these three scenarios are 75, 42, and 41 if the study were halted when the boundary was reached.

Table 14-1: Phase II DLT Monitoring Rule

# Patients Treated	# DLTs	# Patients Treated	# DLTs
1 – 5	-		
6 – 9	6	52 – 56	13
10 – 18	7	57 – 61	14
19 – 26	8	62 – 66	15
27 – 33	9	67 – 70	16
34 – 39	10	71 – 75	17
40 – 45	11	76 – 79	18
46 – 51	12	80	19

Toxicity monitoring for Stratum 4 will be independent of that for Strata 1 through 3. The primary endpoint will be DLT occurring any time pre-surgery through the end of the first course following surgery. The monitoring bounds describe in Table 14-1 will be used. If the number of DLTs equals or exceeds the number in the table, or if at least 5 patients have been treated on stratum 4 and the nominal rate of DLT exceeds that currently observed in strata 1 through 3 combined, the stratum will be suspended to accrual pending review of toxicities by the study committee, in consultation with the DSMC, to determine whether the stratum should continue as planned, be amended, or be terminated.

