14.4 Study Design for Phase II and Target Validation

For Strata 1 through 3, the Phase II study is viewed as three distinct Phase II studies, one corresponding to each of the three strata described in section 1. Each will be a single cohort study using best overall response (BOR – section 14.1) as the primary endpoint. While the primary analysis will be in the intent-to-treat (ITT) cohort – i.e., including all patients who are BOR evaluable per section 14.1, target accrual will be in terms of BOR -evaluable patients with **sufficient treatment (BORwST)**, defined as receiving at least 12 weeks of treatment or experiencing disease progression or death prior to 12 weeks. For the Target Validation Stratum 4, tumor resection prohibits evaluation of BOR as described above, so that analysis tumor response in this stratum will be descriptive.

Each of Stratum 1 and Stratum 2, target minimum accrual is 20 eligible BORwST patients, with up to 30 eligible patients allowed to ensure that at least 20 BORwST are accrued. Accrual to strata 1 and 2

will be halted once it is reasonably certain that this 20-patient target will be achieved. In the unlikely case that minimum of 20 BORwST patients is not reached, the study committee will consider whether an amendment to increase accrual is warranted. The accrual rate to Stratum 1 and Stratum 2 is estimated at approximately 1 per month.

For Stratum 3, target minimum accrual is also 20 eligible BORwST patients, with up to 30 eligible patients allowed. Accrual to this stratum will be halted once it is reasonably certain that the target of 20 BORwST patients will be achieved, or once both stratum 1 and stratum 2 have met accrual goals, whichever occurs first.

For Target Validation Stratum 4, accrual will be halted once it is reasonably certain that 20 patients are enrolled with pre- and post-treatment tumor specimens, or once both Stratum 1 and Stratum 2 have met accrual goals, whichever occurs first.

There will be no statistical monitoring rules for halting the study early either for lack of efficacy or futility.

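### The phase II DLT rule's stated properties fit a maximum of 80 patients, not the permitted 40 to 90; the average of 41 should be about 30, and patients 81 to 90 have no boundary

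*Combined protocol and SAP*

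**What the plan says.** Section 14.6 pools strata 1 to 3 for toxicity monitoring and states that "A minimum of 40 and possibly as many as 90 patients will be enrolled in strata 1, 2 and 3 combined". On what is counted, it says: "The primary endpoint for toxicity monitoring will be the occurrence of DLT during the first course of treatment". Accrual is suspended for review when the cumulative number of DLTs reaches the limit in Table 14-1, whose last entry is 19 DLTs at 80 patients.

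The section claims a Type I error of no more than 14% for true DLT rates up to 15%, "at least 80% power to detect DLT rates of 25% or more", and at least 95% power for rates of 30% or more. It adds that "The average numbers of patients that would be treated under these three scenarios are 75, 42, and 41". No maximum sample size is attached to any of these figures.

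Section 14.4 explains the enrolment range. Strata 1 and 2 each aim for at least 20 patients evaluable for best overall response with sufficient treatment (BORwST), and each may take up to 30. For the third stratum: "For Stratum 3, target minimum accrual is also 20 eligible BORwST patients, with up to 30 eligible patients allowed". That stratum closes when its own target is reasonably certain, "or once both stratum 1 and stratum 2 have met accrual goals, whichever occurs first".

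**The concern.** The power of a cumulative boundary depends on how many patients are observed, so one pair of power figures cannot describe every total from 40 to 90. The averages also look wrong on their face. Raising the DLT rate from 25% to 30% should shorten the time to crossing noticeably, yet the stated average falls only from 42 to 41. Finally, the table ends 10 patients before the enrolment ceiling given in the same section.

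This is the only numeric DLT boundary for strata 1 to 3. If the final total is well below 80, a DSMC relying on the stated 80% and 95% would overestimate the chance that the rule flags a DLT rate of 25% or 30%. If accrual passes 80, the section does not say what count should trigger a review.

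**Working it through.** **Inputs, all from Section 14.6.** Limits in Table 14-1 (patients treated: DLTs): 6–9: 6; 10–18: 7; 19–26: 8; 27–33: 9; 34–39: 10; 40–45: 11; 46–51: 12; 52–56: 13; 57–61: 14; 62–66: 15; 67–70: 16; 71–75: 17; 76–79: 18; 80: 19. There is no limit for patients 1–5 and no entry after 80. DLT rates p are 0.15, 0.25 and 0.30. The enrolment range is 40 (2 × 20) to 90 (3 × 30).

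**Method.** Let f(n, k) be the probability that n patients have been treated with k DLTs and no earlier crossing. Then

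f(n, k) = (1 − p) f(n−1, k) + p f(n−1, k−1).

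At each n, the probability of crossing, P(n), is the sum of f(n, k) over k at or above the limit; those paths are then removed. For a maximum N:

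- Probability of crossing = sum of P(n) for n up to N. This is the Type I error at p = 0.15 and the power at 0.25 and 0.30.
- Average number treated = sum of n P(n), plus N × (1 − probability of crossing).

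The count is checked after every patient.

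**Step 1: the plan's own figures, at N = 80.**

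| DLT rate | Stated probability | Computed | Stated average | Computed |
|---|---|---|---|---|
| 15% | at most 14% | 13.8% | 75 | 74.5 |
| 25% | at least 80% | 83.0% | 42 | 42.7 |
| 30% | at least 95% | 96.9% | 41 | 30.2 |

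The three probability statements hold, and 75 and 42 are within one patient. Only 41 fails to reproduce. Between 25% and 30% the average falls by 42.7 − 30.2 = 12.5 patients, against a stated fall of 1.

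**Step 2: could another reading give 41?** With the printed rule, the average at a 30% rate is 26.9 for N = 40, 29.3 for N = 60, 30.2 for N = 80 and 30.5 for N = 90, and it never exceeds 30.5 in that range. Other readings at N = 80 give these averages at 15% / 25% / 30%:

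- Limit must be exceeded, not just reached: 77.4 / 50.8 / 36.6
- Looks every 5 patients: 75.6 / 46.0 / 33.4
- Looks every 10: 76.6 / 49.9 / 37.3
- Looks every 20: 77.9 / 55.9 / 43.4
- Average among crossing trials only: 40.1 / 35.1 / 28.6

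None gives 75, 42 and 41 together.

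**Step 3: properties by maximum N.**

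| N | Type I at 15% | Power at 25% | Power at 30% |
|---|---|---|---|
| 40 | 7.6% | 56.3% | 80.0% |
| 60 | 12.1% | 75.6% | 93.5% |
| 65 | 12.7% | 78.2% | 94.8% |
| 66 | 13.0% | 79.1% | 95.2% |
| 69 | 13.1% | 79.8% | 95.5% |
| 70 | 13.2% | 80.4% | 95.8% |
| 80 | 13.8% | 83.0% | 96.9% |

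Every N from 40 to 90 was scanned. The 95% claim first holds at 66 and the 80% claim at 70; both hold at every larger N. At N = 40, solving for the DLT rate gives 30.0% for 80% power and 36.2% for 95% power.

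**Step 4: patients 81 to 90.** The chance of reaching patient 81 without crossing is 1 minus the N = 80 probability: 86.2% at a 15% rate, 17.0% at 25% and 3.1% at 30%. At N = 90 the Type I error depends on what is assumed after 80:

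- No limit: 13.8%
- Limit held at 19: 15.3%
- Extension (a), 19 through patient 82, 20 for 83–86, 21 for 87–90: 13.975%, with power 84.5% at 25% and 97.6% at 30%
- Extension (b), 19 through patient 84, 20 for 85–88, 21 for 89–90: 14.15%, with power 85.1% and 97.7%

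Under all four, the averages at N = 90 are about 83, 44 and 30.

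**The case against.** The best defence is that nothing operational is wrong up to patient 80. The endpoint, count, limit and action are all stated, and no limit changes if 41 becomes 30. The 41 is descriptive, and correcting it shows the rule reacting sooner at a 30% rate than claimed. The table ends at 80 and the error rates agree with that, so the properties appear to have been calculated correctly for 80 and reported without saying so. Any fixed boundary has less power when fewer patients are observed, and fewer are then exposed. Reaching patient 81 needs an average of 27 per stratum (81 / 3), above the target of 20, and is unlikely without a crossing at the higher DLT rates. Crossing only suspends accrual for review, and DLT reporting, weekly safety review, the DSMC and the medical monitor continue throughout (Sections 12.2 to 12.5).

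These points are correct and limit the practical harm. They do not rescue the text. A reader cannot tell that the power figures assume 80 patients. Totals below 66 or 70 are also not remote: three strata closing near 20 each give about 60, and stratum 3 may close sooner. The ceiling of 90 is the plan's own figure, so its table should reach that number or the ceiling should come down.

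**Conclusion.** The concern holds. One stated number is wrong: the average of 41 at a 30% DLT rate should be about 30, an overstatement of roughly a third (41 / 30.2 = 1.36). The two power claims hold only from 66 patients (30% rate) and 70 patients (25% rate), within a permitted range that starts at 40, where the powers are 80.0% and 56.3%. Patients 81 to 90 have no numeric boundary. The Type I claim of at most 14% stands at every maximum up to 80, and at 90 if the table is read as printed with no limit after 80.

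The calculation assumes independent patients with a common DLT rate across the pooled strata and a check after each patient's first course. The 41 may be a typing error, but the documents do not show this.

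**What to change.** In Section 14.6:

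1. State that the quoted properties assume a maximum of 80 patients, and report Type I error, power and average number treated at 40, 60 and 90 as well.
2. Replace 41 with about 30.
3. Either cap combined accrual to strata 1 to 3 at 80, or extend Table 14-1 to 90 and restate all properties, including the averages. Extension (a) keeps the claim of at most 14% (13.975%); extension (b) needs it changed to about 14.2%. Both are worked illustrations, and the choice belongs to the study committee and the DSMC.

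The cost is corrected text plus either one sentence for the cap or one or two table rows, with no added patients. The stated power at smaller totals will look less favourable. A cap gives up the last 10 places. Extension (a) has about 0.6 points less power at a 25% rate than (b) (84.5% against 85.1%).

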15. PUBLICATION PLAN

Timely publication will be the responsibility of the principal investigator. No data should be submitted for presentation at public meetings or in abstract form without approval of the principal investigator. Guidelines will follow the rules for publication for the University of Southern California and Children's Hospital Los Angeles.

The results should be made public within 24 months of the end of data collection, sooner if possible. If a report is planned to be published in a peer-reviewed journal, then that initial release may be an abstract that meets the requirements of the International Committee of Medical Journal Editors. A full report of the outcomes should be made public no later than three (3) years after the end of data collection.

Appendix I: LIST OF MEDICATIONS WITH POSSIBLE CYP INTERACTIONS TO BE USED WITH CAUTION

CYP2C19 Inhibitors	CYP2C19 Inducers
cimetidine esomeprazole felbamate fluoxetine fluvoxamine isoniazid ketoconazole lansoprazole omeprazole oral contraceptives pantoprazole ticlopidine voriconazole	efavirenz rifampin ritonavir St. John's Wort
CYP1A2 Inhibitors	CYP1A2 Inducers
aminodarone * cimetidine efavirenz fluoroquinolones fluvoxamine* ticlopidine	carbamazepine tobacco rifampin char-grilled meats
CYP 2B6 Substrates	
artemisinin bupropion cyclophosphamide efavirenz ifosfamide ketamine meperidine methadone nevirapine propofol selegiline	

*Indicates strong/moderate inhibitor. Refer to the following website for a complete list:

<http://medicine.iupui.edu/clinpharm/ddis/clinical-table>

Appendix II: MEK162 ADMINISTRATION

Dosing: The study drug will be administered based on body surface area and should be calculated approximately monthly.

Premedication: None required.

Route of Administration: MEK162 will be administered orally BID, as a suspension prepared by the on-site pharmacy (Appendix XVI), or as a tablet. Co-administration of both tablet and suspension is not permitted, but patients may switch from one form to the other at beginning of a cycle, or at the time of a dose-level change. Administration of suspension via nasogastric or gastrostomy tube is permitted.

Prescribed doses should be taken twice daily, approximately 12 ± 2 hours apart.

If a patient vomits at any time after dosing, the dose of study drug should not be re-administered. Doses of study drug omitted for AEs or any other reason should not be made up later in the day, or at the end of the dosing period.

Appendix III: MOLECULAR ANALYSIS

Due to the rapid development of techniques for protein, lipid and DNA/RNA analysis, newer approaches to those discussed below will be incorporated or substituted where appropriate. All samples should be shipped to [name].

[name], PhD
C/O [name]
Dana-Farber Cancer Institute
[name]
[name]
[name] [contact]
[name]: [name]
[contact]
Email: [contact]
Email: [contact]

Tissue Analysis: Required Tissue Analysis:

- **Oncopanel sequencing**
 - Oncopanel sequences ~500 genes known to be associated with cancer and includes the ability to detect selected translocations and copy number variation. This assay requires 10 formalin fixed paraffin embedded (FFPE) unstained slides with a minimum of 50% viable tumor nuclei and mean depth of coverage is 200X.
- **Oncoscan copy array**
 - Oncoscan copy arrays will be used to survey the DNA copy-number variations across the genome. This requires a minimum of 80ng of genomic DNA. Please send 10 unstained slides with at least 50% viable tumor, and more cellular areas are preferred.

Exploratory Tissue Analysis (if enough tissue available):

- Agilent Array CGH (substitute for Oncoscan if needed):
Array CGH analysis will be performed using paraffin tissue. This array analysis will be directed by [name] from the Department of Neuropathology and will be performed at Brigham and Women's Hospital CAMD.
- OncoPanel:
OncoPanel analysis will be conducted at the Brigham and Women's Hospital Center for Advanced Molecular Diagnostics using DNA derived from paraffin archival tissue. This unique technology allows rapid identification of known mutation within tumor suppressor genes, oncogenes and other major regulators of cellular proliferation.. Results from the OncoPanel may be returned to the patient's chart only if performed in a CLIA-certified lab; this information will be maintained with linkers to the database containing an abstraction of the patient's medical record and the database containing the results of the histopathologic analysis.

- **Additional Sequencing:**
Sequencing, such as whole genome, whole exome, and RNA sequencing to form a more comprehensive view of the genomic changes in tumor tissue may be performed. If tissue is available for this testing such whole genome, whole exome, or RNA sequencing will be conducted at the Broad Institute, in the lab of [name].
- **FISH Analysis:**
FISH analysis has become a routine method for the rapid evaluation of areas of chromosomal region gain or loss. This method uses standard paraffin sections and can be used to examine any chromosomal region that has been identified in the screens above.
- **Methylation Array:**
Methylation array is a new technology that examines the regulation of gene expression at the chromosomal level rather than the DNA, RNA or protein level. Some pediatric tumors may result from the maintenance of gene expression that should have been silenced, or conversely as a result of the failure of an inhibitory gene product to be expressed at the correct time or location rather than by mutation. Methylation array survey the genome for regions that are differentially regulated compared to normal controls. This methodology for methylation analysis is just now becoming available and will be performed if tissue permits.
- **RNA Analysis:**
The frozen tissue obtained will be processed using standard techniques for nucleic acid isolation. Total RNA will be processed for labeling and hybridization to the Affymetrix U133 Plus 2.0 array that contains probes for over 47,000 transcripts and variants including 38,500 well-characterized human genes. For limited amounts of starting material, less than 5 µg of RNA and less than 500 ng of DNA, an amplification step will precede labeling. As new chips become available, they may be substituted for those listed above.

Blood Analysis:

- **Genomic Blood**
 - Blood will be used as genomic normal control to compare to OncoPanel, whole exome, whole genome and gene expression arrays.
 - Peripheral blood serum will be used for exploratory analysis of proteins, lipids, and DNA/RNA

*CSF Analysis***CSF Sample Preparation and Analysis:**

- In order to assess the molecules in the CSF of patients with tumors, cell-free DNA analysis will be conducted at the Broad Institute.

Material from the Buffy coat will be used as controls for the molecular and genomic analyses including sequencing, whole exome, whole genome and gene expression arrays. Plasma will be used for exploratory analysis of proteins, lipids, and DNA/RNA.

[name], PhD
C/O [name]
Dana-Farber Cancer Institute

[name]
[name]
[contact]
[contact]
Email: [contact]

Appendix IV: SPECIMEN COLLECTION, PROCESSING AND STORAGE

Specimen collection and shipment

Patients enrolled on this study may provide specimens and/or clinical information. All specimens will be collected and processed according to site-specific banking procedures. All samples collected under this protocol/consent document will be tracked in the ODQ Neuro-Oncology database at Dana-Farber Cancer Institute.

It is mandatory to contact [name] and [name] prior to shipment to confirm proper materials are sent.

Tumor Tissue: Fresh Frozen Tumor Material

Collection: Tissue will be collected from any patient undergoing neurosurgical procedures as defined in this protocol with patient consent. One “green pea sized” specimen from previously banked snap frozen primary tumor material, regardless of time from surgery, should be rapidly transferred (without thawing) from long term frozen storage to a Styrofoam box filled with 7-10lbs of dry ice for shipment.

Shipment: Samples should be submitted in 1.5mL standard size Cryovials containing the tumor material and labeled according to table 8-2. Please ship in a Styrofoam box (minimum suggested internal dimensions of 30 cm x 30 cm x 30 cm) with 7-10lbs of dry ice. Please include all items on transmittal form including de-identified pathology report from current surgery and any prior surgeries, along with any additional molecular or genetic testing results previously generated. Ship to [name] laboratory in Boston. Follow instructions on transmittal form and confirm shipment with [name] and [name].

Tumor Tissue: FFPE

Collection: The “best block” should be identified for advanced studies by the local pathologist. The block must contain viable tumor with greater than 50% tumor nuclei, less than 30% necrosis, and the tissue fragment size in total ~0.5cm in diameter. The block should contain sufficient tissue to provide 40 standard 5 micron FFPE slides for the planned advanced studies. If you are unable to send a block, please send 20-40 unstained slides and 1 H&E.

Shipment: Slides and blocks should be sent at room temperature in secure slide or block containers in a padded envelope. Please label according to table 8-2. Please include all items on transmittal form including de-identified pathology report from current surgery and any prior surgeries, along with any additional molecular or genetic testing results previously generated. Ship to [name] laboratory in Boston. Follow instructions on transmittal form and confirm shipment with [name] and [name].

Blood

Pharmacokinetic Blood

Collection: 2ml of blood collected in EDTA as indicated in Table 8-1. The tubes will be kept in an ice water bath after blood collection. Within 30 minutes, the tubes will be centrifuged between 3°C and 5°C for 10 minutes at approximately 1500g. Immediately after centrifugation, transfer at least 0.5ml of plasma into a 2ml polypropylene screw-cap tube. Place the tube in a freezer ≤-70°C until shipment.

Shipment: Samples should be submitted in 2ml polypropylene screw-cap tubes as per Section 8.0. Please ship in a Styrofoam box with 7-10lbs of dry ice to QPS Sample Coordination in Delaware, following the instructions on the transmittal form.

Biomarker Blood

Collection: 10ml of blood collected in Cell-Free DNA BCT Streck tube as indicated in Table 8-2 and processed per Section 8.0.

Shipment: Samples should be submitted in 10mL BCT Streck tubes labeled as per table 8-2. Store at room temperature up to 72 hours before shipping. Ship in a padded envelope or other secure packaging at room temperature within 72 hours of collection to [name] laboratory in Boston. Follow instructions on transmittal form and confirm shipment with [name] and [name].

Pharmacodynamic Blood

Collection: 6ml of blood collected in EDTA at time-points as indicated in Table 8-2. Whole blood must be aliquoted into as many 1.5mL standard cryovials (~1mL per tube) as needed. Blood should not be processed further and placed in a freezer -80°C until shipment.

Shipment: Samples should be submitted in 1.5mL standard cryovials labeled as per table 8-2. Samples should be shipped in a Styrofoam box with 7-10lbs of dry ice to [name] laboratory in Boston. Follow instructions on transmittal form and confirm shipment with [name] and [name].

CSF

Collection: CSF can be collected per institutional standards in a sterile, screw top tube and then transferred to a 10mL Cell-Free DNA BCT Streck tube. Store at room temperature up to 72 hours and shipment.

Shipment: in secure package at room temperature to [name] laboratory in Boston. Follow instructions on transmittal form and confirm shipment with [name] and [name]. Ensure tubes are de-identified and labeled with protocol number, patient ID, and draw date. Make note of time at which CSF was collected.

Urine

Collection: in sterile collection cup adding 10-20% volume of Streck Cell-Free DNA Urine Preservative to sample (i.e. 3mL preservative to 30mL urine), Secure cap tightly and gently invert container 5 times to make sure it is well mixed. Transfer to 50 mL conical tube. Store at room temperature up to 72 hours.

Shipment: in secure package at room temperature to [name] laboratory in Boston. Follow instructions on transmittal form and confirm shipment with [name] and [name]. Ensure tubes are de-identified and labeled with protocol number, patient ID, and draw date. Make note of time at which urine was collected and at which preservative was added.

Blood sample volume

The maximum blood volume drawn for all research studies should be no more than 2mL/kg in any one 24-hour period, and 4mL/kg in any one 30-day period, unless otherwise specified by institutional guidelines. In small children for whom the required sample volume would exceed the maximum allowance, the volume of individual samples should be reduced. Questions regarding sample size reduction can be discussed on a case by case basis with the study chair.

Specimen processing, storage, and coding

All specimens will be processed according to site-specific banking procedures; exceptions are made for samples that are required to go directly to the researcher and/or laboratory for immediate processing. The amount of each of the following samples will be tracked in the ODQ Neuro-Oncology database at the Dana-Farber Cancer Institute or other in-house tracking system. All biological samples will be coded with an internal numbering system to ensure patient confidentiality. The samples will be stored and distributed to researchers with this numbering code as the only identifier.

Specimen that circumvent the tissue bank and go directly to the researcher or laboratory

Samples that are required to go directly to the researcher and/or laboratory for immediate processing can be collected and not be entered in the bank: i.e. blood and tissue that requires immediate processing beyond the scope of the bank, such as for the creation of cell lines, if it is codified. All samples, including those that go for immediate processing outside the bank, are to be logged into and out of the ODQ Neuro-Oncology database.

Specimen tracking of all samples collected and distributed under this protocol

All samples collected and distributed for the use of future research studies are to be tracked, and logged into and out of ODQ DFCI database. The database will be able to generate reports of what is available in storage, and provide a history of samples obtained and distributed.

If the formal tissue bank wishes to track samples using an internal tracking system with similar features, this will be noted with the description of the bank in Appendix XII. If this option is chosen by a facility, it should be noted that samples obtained using this protocol that are not logged into the bank's internal tracking system, for instance samples which circumvent the tissue bank are to be tracked

in this database. The internal tracking system must track not only what is in store, but provide a history of samples obtained and distributed. The ODQ Neuro-Oncology database also has the useful capability of allowing samples to be reserved, succeeding permission from the respective oversight committee.

Samples after a patient withdraws from the study

Should a participant or his/her legally authorized representative or his/her next of kin withdraw consent from the study, any unused tissue specimens will be removed from the tissue bank and will be discarded. Tissue, its derivatives, and results from samples previously obtained and distributed to third parties (outside of the respective main tissue bank) will not be recalled or destroyed.

Coding of samples given to investigators

All biological samples will be coded with a numbering system to ensure patient confidentiality. The samples will be stored and distributed to researchers with this numbering code as the only identifier on the sample.

QPS (Pharmacokinetic Blood):

QPS Sample Coordination

[name]

[name]

[name]

[name] (all other samples):

[name] C/O [name]

Dana-Farber Cancer Institute

[name]

[name]

